15.1. Response criteria

15.1.1. Prevalence of periportal fibrosis of the liver

A WHO Niamey Protocol for Ultrasound in Schistosomiasis pattern score of C, D, E or F will be considered as presence of periportal fibrosis. This will be measured during baseline activities, and at 2-years. A 20% difference in prevalence between the control and intervention arm at 2-years of intervention will be considered a success.

15.1.2. Schistosoma mansoni infection intensity

S. mansoni faecal egg counts as determined from Kato Katz smears will be used to calculate infection intensity. A statistically significant difference between control and intervention arm, with an alpha of 0.05, and 80% power will considered a success.

16. Storage and Analysis of Samples

Stool samples will be collected and processed for egg counts by Kato Katz. Stool samples will also be processed for hatching of the miracidial stage of the parasite for genetic characterisation, the exploratory outcomes.

Urine samples will be collected and tested using a point-of-care rapid diagnostic test for *Schistosoma mansoni*.

Blood is to be drawn into EDTA, heparin anti-coagulants and for sera by a skilled phlebotomist. Whole blood cell cultures will be set up from the heparin aliquot and plasma harvested from the EDTA aliquot. Plasma and culture supernatants will be stored between -15°C and 25°C in the trial site laboratory. Sera will be stored between -60°C and -80°C. Shipment to the analysing laboratory will be on dry ice or in liquid nitrogen vapour. Upon receipt, plasma and cell culture supernatants will be stored at between -60°C and -80°C in a specialised freezer until assays are to be processed.

Peripheral blood mononuclear cells (PBMC) will be cryopreserved in liquid nitrogen vapour at the study laboratory situated within Hoima District, and shipped to the analysing laboratory where they will be stored in liquid nitrogen tanks.

Blood products, urine and stool samples will be collected for future pathogen specific research, and host-pathogen research. Unprocessed stool samples will be stored in at VCD-Uganda, blood products, urine and one aliquot of stool sample products will be shipped to University of Cambridge. They will remain the property of VCD-MoH Uganda. Participating laboratories will be able to request access to these samples. Researchers outside of the trial will have access on a case-by-case basis. These requests will only be granted if the research questions is in line with the participant information sheet. Transfer will be considered by a Material Transfer Committee, including an independent researcher. These samples will be held for a maximum of 15-years, after which they will be destroyed. They will be stored according to UK Human Tissue Act regulation standards, irrespective of where they are stored. All samples will be linked anonymised.

ISRCTN Number: 16994599 Page 32 of 48

17. Statistics

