8.6.3. Exploratory outcome measure

An exploratory secondary use of the trial data will be mathematical modelling of predicted long-term success of trial strategy. One year interim assessments of infection levels are to be taken to improve the fit of these models.

An exploratory outcome measure is the *S. mansoni* egg reduction rate, measured post treatment at baseline + 4 weeks and 2-years + 4 weeks, with accompanying parasite genetic/genomic characterisation. Processing of stool samples for parasite isolation will solely be conducted on samples received from participants who tested positive for *S. mansoni* infection using a point-of-care urinary dipstick that detects circulating cathodic antigen (CCA).

An exploratory outcome measure is host immuno-pathological responses to the eggs of the parasite. This will be measured at baseline, and if local conditions permit at the 2-year follow-up.

9. Community, School and Trial Team COVID-19 precautions

All Trial activities carried out by the trial team members will be performed following the COVID-19 precaution national guidelines and the trial Risk Mitigation Plan for the duration of the pandemic in Uganda. Any future national guidelines issued by the Ugandan Government will be reviewed by the Sponsor alongside the trial Risk Mitigation Plan and implemented as required.

ISRCTN Number: 16994599

10. Selection and withdrawal of participants

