11.2.3 Returns and destruction

All praziquantel not used within the trial will be returned to Trial site co-ordinator, [name], Vector Control Division – Ministry of Health, Uganda.

12 Procedures and assessments

All procedures will be undertaken within the communities. Ultrasonography examinations and phlebotomy will be conducted within the schools or local community trial site location, when the schools are not available due to COVID-19 restrictions or any other government restrictions, including other infectious diseases. Stool and urine samples will be collected in a sensitive manner from participants in the school setting or house-hold to house-hold dependent upon COVID-19 or other government restrictions. Annual treatments will be dispensed after scheduled sample collection and ultrasonography examinations in the school setting, local community trial site location or house-hold to house-hold dependent upon COVID-19 or other government restrictions. Intervening treatments will be dispensed by the trial team during visits to the participating primary schools, community trial site location or house-hold to house-hold dependent upon COVID-19 or other government restrictions. Treatment will be observed by trained members of the trial team, and a 24-hour post-treatment follow-up will be conducted by a trained health worker to record treatment sideeffects. The collected blood and stool samples will be processed as initially planned. Dependent upon COVID-19 or other government restrictions, and where possible, samples may be frozen for analysis at a later date.

When COVID-19 or other government restrictions are lifted it is intended that trial activities which directly involve the participants will be carried out in the participating primary schools as initially planned. The alternative locations for trial activities are to facilitate the conduct of trial activities whilst adhering to the COVID-19 or other government restrictions, the National Guidelines for Conduct of Research during coronavirus Disease 2019 (COVID-19) Pandemic, July 2020, UNCST, Government of Uganda and the FibroScHot Risk Mitigation Plan.

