12.3.2. Exploratory outcomes

Sample collections for the exploratory outcomes to be carried out where local conditions permit and involve:

Stool samples 4-week post-treatment egg reduction egg counts

Urine samples Pre-treatment and 4-week post-treatment CCA urinary

dip-stick diagnosis of *S. mansoni*. Parasites to be hatched

from stool samples for those positive by CCA.

Blood sample 8ml by phlebotomy for cellular and cytokine response

measurement.

ISRCTN Number: 16994599

All assessments are non-invasive (ultrasonography and stool collection), or considered of minor risk (phlebotomy).

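### Section 16 sets site storage of plasma and culture supernatants at -15°C to 25°C, most likely a missing minus sign; as written it permits unfrozen storage of the exploratory immune-response samples

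*Protocol*

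**What the plan says.** The protocol's Section 16 (Storage and Analysis of Samples) gives one storage condition for each blood product and stage:

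- Plasma and supernatants at the site: "Plasma and culture supernatants will be stored between -15°C and 25°C in the trial site laboratory".
- Sera: "Sera will be stored between -60°C and -80°C".
- Transport: "Shipment to the analysing laboratory will be on dry ice or in liquid nitrogen vapour".
- Plasma and supernatants at the analysing laboratory: "Upon receipt, plasma and cell culture supernatants will be stored at between -60°C and -80°C in a specialised freezer until assays are to be processed".
- Mononuclear cells from peripheral blood are kept in liquid nitrogen vapour at the study laboratory and in liquid nitrogen after shipment.

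The blood is drawn for an exploratory purpose. Section 12.3.2 describes it as "8ml by phlebotomy for cellular and cytokine response", collected where local conditions permit. Section 8.6.3 states: "An exploratory outcome measure is host immuno-pathological responses to the eggs of the parasite". It is measured at baseline and, conditionally, at 2 years. Section 16 also keeps blood products for future research for up to 15 years.

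Section 12 adds, for periods of government restriction and where possible, that "samples may be frozen for analysis at a later date". It gives no temperature.

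**The concern.** An instruction that tells a field laboratory how to hold samples should leave only acceptable conditions inside its limits. This one leaves frozen, refrigerated and room-temperature storage equally compliant, and it allows a sample to move back and forth across its freezing point. The protocol sets no limit on how long samples may wait at the site.

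The consequence is mainly one of detection. Section 23 defines a deviation as a departure from the approved protocol. An aliquot held at 20°C is not a departure from Section 16 as worded, so nothing obliges anyone to record it. The analyst of the immune-response data would then have no marker to separate a degraded aliquot from a child with a genuinely low response. Baseline and 2-year samples are held in different periods, so unequal handling could look like a change in host response. Pre-treatment blood cannot be redrawn once treatment has begun.

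**Working it through.** The protocol has no calculated figure to reproduce here. The check is a comparison of the stated conditions plus simple arithmetic on the limits.

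**1. Width of the site range (Section 16).**
- As written: 25 - (-15) = 40 degrees. Taking freezing as near 0°C (an assumption), 25 of the 40 degrees, or 25/40 = 62.5%, leave the sample liquid.
- With a minus sign before 25: -15 - (-25) = 10 degrees, frozen throughout.

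**2. Fit with the rest of the paragraph.**

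| Material and stage | Stated condition | Frozen throughout? |
|---|---|---|
| Plasma, supernatants, at site | -15°C to 25°C | No |
| Sera | -60°C to -80°C | Yes |
| Shipment | Dry ice or nitrogen vapour | Yes |
| Plasma, supernatants, after receipt | -60°C to -80°C | Yes |
| Mononuclear cells | Liquid nitrogen vapour, then liquid nitrogen | Yes |

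The site range is the only entry that reaches above zero. Its upper limit is 25 - (-60) = 85 degrees warmer than the warmest temperature allowed for the same material after receipt.

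**3. Order of the limits.** Both other numerical ranges in the section put the warmer limit first (-60, then -80). A range of -15 to -25 follows that pattern; -15 to 25 reverses it. This favours a dropped sign.

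**4. Does any other text settle it?** No other sentence narrows the range. The amendment history (Appendix 3, version 2) records that the Section 16 storage range was widened but gives no values, so it neither confirms nor rules out a positive 25.

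**5. Could the sign have been lost in text extraction?** The check was made on text extracted from the PDF. A line-end hyphen has disappeared in Section 12 (in the word for side-effects), so such a loss is possible. Against it, the other minus signs in Section 16 survived, and an approximate reconstruction of the line breaks does not place a line end before this figure. Loss is unlikely but not excluded.

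**6. What is exposed.** Section 16 harvests plasma from the EDTA aliquot and sets up whole-blood cultures from the heparin aliquot, so these are the materials affected. Section 8.3 plans 600 children and anticipates enrolling up to 750. Those figures are ceilings: blood collection is conditional and the protocol does not count aliquots. The primary outcome comes from ultrasound and the secondary from Kato-Katz egg counts, so neither depends on these samples.

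**The case against.** The strongest reply is that this is a typographical slip whose intent any laboratory would recognise, affecting only a conditional exploratory outcome. Most of that stands. The frozen transport and deep-frozen storage on arrival do point to frozen site storage as the intent, so it should not be described as a deliberate room-temperature design.

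Three stronger readings are tempting, and the documents support none of them.

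- A reader might infer that Section 16 contradicts itself. It does not strictly do so. Sera are a different material, and the -60°C to -80°C rule for plasma and supernatants applies at a later stage and in a different laboratory. Both rules could be followed in sequence; the site range is out of keeping with its neighbours rather than incompatible with them.
- A reader might infer bias in the treatment comparison. Children are randomised individually, stratified by school (Sections 10.3 and 12.3.3), and nothing suggests that storage differs by arm. A handling shift between collection periods would touch all three arms and would not by itself create a between-arm effect.
- A reader might infer that the immune-response data will be lost. The protocol gives no stability data and no evidence of how samples were actually held, so neither the occurrence nor the extent of degradation can be claimed.

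It is also fair to say that holding times and temperature monitoring often sit in laboratory instructions that are not shown here; their absence from the protocol is not part of this point. What the reply does not remove is that the approved text is the operative rule, and it calls an unfrozen sample compliant.

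**Conclusion.** The point holds as a wording error in an operative handling rule. As written, Section 16 allows a 40-degree range reaching room temperature; the probable intended range is 10 degrees and wholly sub-zero. If 25°C above zero was in fact meant, the sentence still needs reconciling with the frozen chain around it.

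The reach is limited to the exploratory immune-response outcome and the retained plasma and supernatants. The harm at stake is unflagged degradation, appearing as noise or as an apparent change from baseline to 2 years. Its size cannot be stated from the documents. Sera, mononuclear cells, the primary outcome and the secondary outcome are unaffected.

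The conclusion assumes that the extracted text matches the source document at this figure. If the source shows the minus sign, the point falls away.

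**What to change.** 1. Check the figure against the source document and confirm the intended range with the sponsor.
2. If the error is in the source, correct the Section 16 site range to the intended wholly sub-zero one (for example -15°C to -25°C, if that is what was meant) and align the site laboratory instructions.
3. State that any reading above the corrected upper limit is an excursion and flags the aliquots concerned.
4. For samples already stored, use whatever site temperature or sample records exist to flag aliquots held above the corrected limit. Exclude them from the immune-response analysis, or run a sensitivity analysis without them. Section 18.2 lists a sample log among the source data but no temperature log, so it may not be possible to classify every aliquot; those that cannot be classified should be reported as such.

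The text change is a single character, but Section 20.3 requires sponsor agreement and ethics committee review for an amendment; it could travel with another administrative change. The real cost is the look-back through site records and the possible loss of some aliquots from the exploratory analysis.

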17.1. Statistical methods

The primary analysis will estimate the absolute difference between the arms in terms of the rate of periportal fibrosis using logistic regression on the absolute difference scale, adjusting for baseline covariates, including school, fibrosis score and egg count. Treatment effect estimates and 95% confidence intervals will be reported; formal hypothesis testing will compare the two-sided p-values for all three pairwise comparisons to a nominal significance level of 1.66%, as a Bonferroni correction to preserve the overall significance level at 5%.

Secondary endpoints will be analysed using regression tools to compare arms, adjusting for covariates, but tailoring the model to the form of the endpoint (continuous, binary, time-to-event) as required.

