8.5. Trial Objectives

8.5.1. Primary objective

To compare the effect of 2x and 4x treatments annually with praziquantel to the standard 1x annual treatment on the prevalence of *Schistosoma mansoni* associated periportal fibrosis of the liver.

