17.2. Number of Participants to be enrolled

Berhe et al 2008 (20) reported a 47.7% resolution rate of grade C to non-periportal fibrosis scores of A and B and 24.6% resolution rates of D scores to scores A and B. Extrapolating this success rate onto our preliminary data, we would expect 35% less of the children in a successful intervention arm to have periportal fibrosis after 2-years intervention than those in the control arm. However, Berhe et al also reported geographical differences in resolution, with higher transmission villages having poorer resolution. We therefore propose a minimum 20% absolute difference in prevalence of periportal fibrosis between the control and intervention arms to be a clinically significant outcome. Based on preliminary data we assume an incidence rate of scores C-F of 80% in the control arm. With a Bonferroni correction to allow any pairwise comparison between the three arms, testing at a 1.66% significance level, a total sample size of 450, 150 per arm, would provide 92% power to detect an absolute reduction of 20%. In previous Lake Victoria fishing community observation studies, failure to follow-up has been as high as 35%. The communities on Lake Albert are more stable ([name], pers. comm.) but to minimise failure to follow-up, selection is restricted to children in P1 to P4, retaining the cohort within the primary school structure over the two years of the study, and an inclusion criteria of born or resident in the village for >2yrs, displaying stability of their household within the village is included. A failure to follow-up of 25% is included in the final study numbers. Six hundred primary school-aged children will be enrolled into the study, with 200 randomised into each of the three intervention arms. Given the disruption caused by the COVID-19 pandemic to the communities from which the participants for this trial are identified, we anticipate this may require up to 750 participants to be enrolled to obtain the sample size of 600; however we will continue to recruit participants until target participant completion is achieved.

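### The flat 1.66% Bonferroni rule is valid, but a step-down rule for three arms gains power at the same overall 5% and costs only wording

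*Protocol*

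**What the plan says.** Section 17.1 (Statistical methods) fixes the multiplicity rule for the primary analysis: "formal hypothesis testing will compare the two-sided p-values for all three pairwise comparisons to a nominal significance level of 1.66" per cent, described "as a Bonferroni correction to preserve the overall significance level at 5" per cent. On estimation, the same sentence says "Treatment effect estimates and 95% confidence intervals will be reported", with no mention of adjusting them.

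Section 17.2 sizes the trial on the same rule: "With a Bonferroni correction to allow any pairwise comparison between the three arms, testing at a 1.66% significance level". It adds that "we assume an incidence rate of scores C-F of 80% in the control arm", takes a "minimum 20% absolute difference in prevalence of periportal fibrosis between the control and intervention arms" as the clinically significant difference, and concludes that "a total sample size of 450, 150 per arm, would provide 92% power to detect an absolute reduction of 20" per cent.

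The primary objective (section 8.5.1) is "To compare the effect of 2x and 4x treatments annually with praziquantel to the standard 1x annual treatment", which makes two control comparisons. The synopsis (section 4) gives the wider purpose of finding the most effective frequency. The protocol contains no step-down, closed or hierarchical procedure.

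**The concern.** Flat Bonferroni holds every comparison to 1.66%, whatever the other comparisons have shown. With exactly three arms that is stricter than it needs to be. Two of the three equalities cannot be true while the third is false, because two equalities imply the third. Once one equality has been rejected, at most one of the other two can still be true, and testing both at 5% cannot push the family-wise error above 5%.

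What is at stake is power on the second and third comparisons. The objective names two control comparisons, and choosing between frequencies needs more than one rejection. The loss therefore falls on the results that would separate one frequency from another, not on the chance of finding anything at all.

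There is a smaller reporting side. The intervals are at 95% and the test is at 1.66%, so a 95% interval can exclude zero when the formal test has not rejected.

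**Working it through.** **Inputs.** Section 17.2: control prevalence 80%, difference 20 points (so 60%), 150 evaluable per arm, two-sided level 1.66%. Section 12.3.3: allocation 1:1:1. Prevalences of 65% and 70% below are assumptions, not protocol values.

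**1. The plan's own figures.** The overall level is 3 × 1.66% = 4.98%, a harmless rounding down. Power uses the pooled two-proportion z test:

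- SE under the null = √(2 × 0.70 × 0.30 / 150) = 0.0529
- SE under the alternative = √((0.80 × 0.20 + 0.60 × 0.40) / 150) = 0.0516
- critical value for two-sided 1.66% = 2.395
- power = Φ[(0.20 − 2.395 × 0.0529) / 0.0516] = Φ(1.42) = 92.2%

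The stated 92% reproduces. The enrolment target does too: 450 / 0.75 = 600.

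**2. Why the step-down rule controls the error.** The rule compares the smallest p-value with 5%/3 and stops if it is not rejected. If it is rejected, the other two are each tested at 5%.

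- All three equalities true: a false rejection needs the smallest p ≤ 5%/3, with probability at most 3 × 5%/3 = 5%.
- Exactly one true: it is never tested above 5%.
- Exactly two true: impossible.
- None true: no false rejection can occur.

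Because 5%/3 is not below 1.66% and the later level is higher, the rule rejects everything that the flat rule rejects.

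**3. Size of the gain.** 400,000 simulated trials per scenario, 150 per arm, pooled z tests without covariates:

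| True prevalence 1x/2x/4x | Quantity | Flat 1.66% | Step-down |
|---|---|---|---|
| 80/60/60 (design effect) | each frequency vs 1x | 92.4–92.5% | 95.9% |
| 80/60/60 | both vs 1x | 87.0% | 93.9% |
| 80/60/60 | at least one rejection | 97.9% | 97.9% |
| 80/65/65 (assumed) | both vs 1x | 55.8% | 71.1% |
| 80/65/60 (assumed) | 2x vs 1x | 70.3% | 82.1% |
| 80/70/60 (assumed) | 2x vs 1x | 34.5% | 51.2% |
| 80/80/80 | family-wise error | 4.4% | 4.4% |
| 80/80/60 | false rejection, 2x vs 1x | 1.7% | 5.0% |
| 80/60/60 | false rejection, 4x vs 2x | 1.6% | 5.2% |

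The 5.2% comes from the z approximation, not from the rule. In that scenario a single z test at 5% rejects 60% vs 60% in 1.63% + 3.53% = 5.16% of trials.

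**4. Intervals.** At 80% vs 60% the 95% half-width is 1.960 × 0.0516 = 10.1 points. The interval matching a 1.66% test (98.34%) has half-width 2.395 × 0.0516 = 12.4 points. A given control comparison has p between 1.66% and 5% in about 4.5%, 13% and 17% of trials for true differences of 20, 15 and 10 points. There the 95% interval would normally exclude zero without formal significance.

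Under the step-down rule most of this goes. At 80/60/60, 2x vs 1x has p ≤ 5% in 92.50% + 4.49% = 96.99% of trials and is rejected in 95.91%, leaving about 1.1%. At 80/70/60 the same sum is 34.49% + 17.41% − 51.21%, or about 0.7%.

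**The case against.** The strongest reply is that nothing here is wrong. The protocol names its hypotheses, its level and its error control, and sizes the trial on the same rule. A simple pre-specified Bonferroni correction whose sample size is already provided for is a legitimate choice. That stands, and it is why this is an improvement and not an error.

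The largest gains rest on 10- or 15-point differences, whereas sections 15.1.1 and 17.2 set 20 points as the benchmark. That stands too. At the design effect the gain per control comparison is about 3.5 points, and the chance of any rejection does not change. The 7-point gain for showing both frequencies superior needs no assumption beyond a 20-point effect in both arms.

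The added power also comes from somewhere: with one true equality, its error rate rises from about 1.7% to about 5%. This is correct, and it remains within the overall 5% that section 17.1 sets.

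A reader might infer that 95% intervals beside a 1.66% test give two competing verdicts on the primary outcome. The text does not support that. Section 17.1 separates estimation from formal testing and takes its decisions from p-values only, so this is a matter of labelling. Nor would 98.3% intervals cure it if the step-down rule is adopted. Every rejection that rule adds has p between 1.67% and 5%, so its 98.3% interval would normally include zero. At 80/70/60 that would happen for 2x vs 1x in about 17% of trials.

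Finally, the simulation ignores the planned adjustment for school, baseline fibrosis score and egg count, so its figures are approximate for the planned analysis. The logical dominance in step 2 does not depend on the simulation.

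**Conclusion.** The point holds as an optional efficiency gain. The flat 1.66% rule is valid and the stated power and sample size are correct, but a step-down rule with the same strong 5% control is uniformly more powerful. At the design effect, power to show both frequencies superior to control rises from 87% to 94%, and power for each from about 92.4% to 95.9%. The chance of at least one rejection stays at 97.9%. Larger gains, such as 35% to 51% for 2x vs 1x at 80/70/60, depend on assumed prevalences.

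A reader might go further and conclude that the trial is underpowered or its multiplicity control faulty. The recalculated 92.2% and the 4.98% total level show neither. All simulated figures assume 150 evaluable participants per arm and unadjusted z tests.

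**What to change.** In section 17.1, replace the flat comparison with 1.66% by the following rule. Compare the smallest of the three two-sided p-values with 5%/3. If it is not rejected, stop. If it is, test each of the other two at 5%. Name it as Shaffer's step-down procedure for three arms. Keep the 95% intervals, state that they are unadjusted for multiplicity, and state that conclusions come from the step-down p-values only.

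The sample size in section 17.2 can stand, because the first step is at essentially the level already used and power can only rise.

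The cost is a few sentences in the protocol, carried into the statistical analysis plan, and settled before outcome data by arm are seen. There are two downsides to accept openly: the higher error rate when one equality is true (about 5%, within the stated overall level), and the lack of simple simultaneous intervals matching the step-down test. A sponsor who prefers to keep flat Bonferroni need only add the label on the 95% intervals.
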